6. SAFETY REPORTING AND MEDICAL MANAGEMENT

The Principal Investigator is responsible for ensuring that all staff involved in the study are familiar with the content of this section. The Sponsor's delegate Medical Services will provide an out of hours medical management service; contact details will be provided to Investigators and subjects (to be used only by healthcare professionals in case of emergency).

6.1 Definition of adverse events

An adverse event is the development of any untoward medical occurrence in a subject or clinical study subject administered a medicinal product and which does not necessarily have a causal relationship with this treatment. An AE can therefore be any unfavourable and unintended sign (eg, an abnormal laboratory finding), symptom (for example nausea, chest pain), or disease temporally associated with the use of a medicinal product, whether or not considered related to the medicinal product.

The term AE is used to include both serious and nonserious AEs and can include a deterioration of a pre-existing medical occurrence. An AE may occur at any time, including run-in or washout periods, even if no study treatment has been administered.

6.2 Definitions of serious adverse event

A serious adverse event is an AE occurring during any study phase (ie, run-in, treatment, washout, follow-up), that fulfils one or more of the following criteria:

- Results in death
- Is immediately life-threatening
- Requires in-subject hospitalisation or prolongation of existing hospitalisation
- Results in persistent or significant disability or incapacity.
- Is a congenital abnormality or birth defect
- Is an important medical event that may jeopardise the subject or may require medical intervention to prevent one of the outcomes listed above.

For further guidance on the definition of a SAE, see [Appendix A](#) to the Clinical Study Protocol.

If a subject decides to have surgery to correct a pre-study condition that has not worsened since the ICF was signed or the surgery was planned before the ICF was signed, then the

hospitalisation is not considered an SAE. If however, a new condition occurs or a pre-existing condition worsens and surgery is required, then the hospitalisation is considered an SAE.

6.3 Hy's Law

Cases where a subject shows elevations in liver biochemistry may require further evaluation and occurrences of AST or ALT $\geq 3 \times \text{ULN}$ together with total bilirubin $\geq 2 \times \text{ULN}$ may need to be reported as SAEs. Please refer to [Appendix D](#) for further instruction on cases of increases in liver biochemistry and evaluation of Hy's Law.

6.4 Definition of Adverse Event of Special Interest

An AESI is one of scientific and medical concern specific to understanding biologics and requires close monitoring and rapid communication by the Principal Investigator to the Sponsor/Sponsor's delegate. An AESI may be serious or nonserious.

Adverse Events of Special Interest will be assessed at each visit in the eCRF. The events of interest are serious infections, including non-opportunistic serious infections, opportunistic infections, anaphylaxis, malignancy, herpes zoster, TB (including latent TB), influenza, vasculitis (non-SLE), and MACE (including stroke, acute coronary syndrome, myocardial infarction, or cardiovascular death).

An AESI that meets one of the seriousness outcomes listed in Section 6.2 will be categorised as an SAE for the purposes of follow-up responsibility and safety reporting. A nonserious AESI will be categorised as an AE. For reporting of AESIs, see Section 6.7.

6.4.1 Non-opportunistic serious infection

A serious non-opportunistic infection is any non-opportunistic infection that meets the SAE criteria in Section 6.2. Serious non-opportunistic infection AEs are reported as SAEs. It is expected that culture results and all diagnostic or therapeutic procedure results performed on a subject experiencing a serious non-opportunistic infection will be provided as an SAE update. Nonserious non-opportunistic infections will not be captured as AESIs.

6.4.2 Opportunistic infection

An opportunistic infection is an invasive infection caused by microorganisms that are normally non-pathogenic or rarely pathogenic in individuals with normal immune function or cause an infection of a type or severity not seen in the normal host. Opportunistic infections are categorised as serious and reported as an SAE.

Examples of opportunistic infections that may occur in SLE subjects include: *Herpes zoster* meningoencephalitis, *Salmonella* bacteremia, *Pneumocystis jiroveci* pneumonia or progressive multifocal leukoencephalopathy.

It is expected that culture results and all diagnostic or therapeutic procedure results performed on a subject experiencing a serious opportunistic infection will be provided as an SAE update.

Since anifrolumab is an immunomodulatory agent and the Sponsor needs to understand the safety profile of this IP, including assessment of how anifrolumab may affect resistance to different types of infections, Investigators are asked to undertake appropriate microbiologic identification including culture and report culture results for all subjects who develop serious infections.

6.4.3 Anaphylaxis

Anaphylaxis is a severe, potentially fatal, systemic allergic reaction that occurs suddenly after contact with an allergy-causing substance, such as IP. For the purposes of this study, the definition detailed in [Appendix L](#) is provided as a simple and rapid means to make the diagnosis of anaphylaxis during infusion with IP. This definition was a product of a symposium convened by the National Institute of Allergy and Infectious Diseases and Food Allergy and Anaphylaxis Network ([Sampson et al, 2006](#)).

6.4.4 Malignancy

Malignancy is a neoplasm characterised by cells with abnormal features, uncontrolled rapid growth with invasive and/or metastatic tendencies diagnosed based on pathologic and clinical standards. Understanding risk of developing different malignancies is critical to establishing the benefit-risk profile for anifrolumab. Investigators are therefore requested to obtain biopsy results and have pertinent biomarker and/or genetic testing results performed and to report these for any malignancies reported during the study.

6.4.5 Herpes zoster

Herpes zoster is a viral infection characterised by a cutaneous vesicular eruption on an erythematous base presenting along dermatome(s) and usually associated with prodromal pain. Herpes zoster results from the reactivation of *Varicella zoster* virus; multiple dermatomes may be involved (>3 indicates disseminated disease) and organ or systemic infection may occur (invasive; therefore an opportunistic infection). Polymerase chain reaction (PCR) testing of samples from vesicles, biopsy or other specimens (eg, cerebrospinal fluid) may confirm the presence of *Varicella zoster* virus.

For additional information regarding herpes zoster, refer to the Investigator Brochure. As this is an AESI, the Sponsor will collect information including whether or not subjects have received vaccination for herpes zoster. The herpes zoster vaccine will be captured in the appropriate sections of the CRF.

6.4.6 Tuberculosis

Tuberculosis is a mycobacterial infectious disease generally presenting as cough with systemic symptoms of infection diagnosed by skin test (purified protein derivative), blood test

(IFN- γ release assay), radiographic imaging, body fluid and tissue sampling; presentation may include disseminated or latent disease. An infection may be new (at least conversion of a TB test to positive) or reactivation of dormant disease (new active disease in a previously TB test positive subject without prior evidence of active disease).

- **A bacteriologically confirmed TB case** is one from whom a biological specimen is positive by smear microscopy, culture or rapid diagnostic such as PCR or nucleic acid amplification test (Xpert MTB/RIF).
- **A clinically diagnosed TB case** is one who does not fulfil the criteria for bacteriological confirmation, but has been diagnosed with active TB by a clinician or other medical practitioner who has decided to give the subject a full course of TB treatment. This definition includes cases diagnosed on the basis of X-ray abnormalities or suggestive histology and extra-pulmonary cases without laboratory confirmation. Clinically diagnosed cases subsequently found to be bacteriologically positive (before or after starting treatment) should be reclassified as bacteriologically confirmed.

Bacteriologically confirmed or clinically diagnosed cases of TB are also classified according to: anatomical site of disease; history of previous treatment; drug resistance; and HIV status ([World Health Organisation, 2014](#)).

Latent TB is a mycobacterial infection without clinical, bacteriological findings, or radiologic findings consistent with active TB and a TB blood test such as an IGRA (QuantiFERON-TB Gold) or purified protein derivative skin test that is positive both at the time of provisional diagnosis and on repeat assessment.

Subjects identified with latent TB will be assessed by a local TB specialist to confirm the diagnosis and local SOC that will be used in treatment. If no local guidelines exist for immunocompromised individuals, then CDC guidelines may be followed. Once latent TB is confirmed, treatment must be instituted immediately and no IP may be administered until treatment of latent TB has begun. Additionally, subjects with newly diagnosed latent TB must agree to complete a locally recommended course of treatment for latent TB in order to continue receiving the IP.

6.4.7 Influenza

Influenza is a severe viral infection that includes the following symptoms: temperature greater than 100.8°F (38.2°C), and malaise, headache, or myalgia. It is often accompanied by nausea, vomiting, and diarrhoea, and at least one of the following respiratory symptoms: cough, sore throat, or shortness of breath.

Laboratory criteria for influenza include at least one of the following: isolation of influenza virus from a clinical specimen, detection of influenza virus nucleic acid in a clinical specimen,

identification of influenza virus antigen by direct fluorescent antibody test in a clinical specimen, or influenza-specific antibody response.

A confirmed case of influenza meets the clinical and laboratory criteria for the viral illness. Laboratory confirmation should be done using locally available, rapid, commercial tests approved by Regulatory Agencies and sampling respiratory specimens.

Not all upper respiratory viral infections or gastrointestinal viral infections are influenza. In the case where a subject reports a viral infection severe enough to be considered, in the opinion of the investigator, influenza, a viral test should be performed (if possible) to confirm the diagnosis. Whether or not a test to confirm the diagnosis has been performed, if, in the opinion of the investigator, the subject has had influenza (the specific viral infection), this should be reported as an AESI. If the subject has had a viral infection that is less severe, then this should be reported as an AE only.

6.4.8 Vasculitis (non-systemic lupus erythematosus)

Vasculitis (non-SLE) is defined as an inflammatory disorder of blood vessels involving arteries and/or veins and characterised by characteristic clinical signs/symptoms and diagnosed by biopsy, imaging such as angiography or blood tests such as findings of anti-neutrophil cytoplasmic antibodies consistent with the diagnosis. Underlying causes should be identified, such as medications including investigational drug, infections or systemic inflammatory syndromes, wherever possible. See [Appendix G](#) for a list of vasculitic syndromes excluded from the study.

6.4.9 Major acute cardiovascular events

As a measure of enhanced Pharmacovigilance, an independent Cardiovascular Event Adjudication Committee (CV-EAC) will review deaths (due to any cause) and all SAEs in both the Cardiac and Vascular MedDRA System Organ Classes and all SAEs in the Central Nervous System Vascular Disorders Standard Medical Query for evaluation. The CV-EAC chair may adjudicate some events that do not fall into the above categories.

The CV-EAC will review cases of interest to determine if they meet accepted diagnostic criteria. Causality assessments will not be made by the CV-EAC, nor will the committee possess governance authority. The CV-EAC will be blinded regarding any information relating to the randomisation group.

6.5 Recording of adverse events

6.5.1 Time period for collection of adverse events

Adverse events and SAEs will be collected from the time of signature of the ICF until the end of the subject's participation in the study. Serious adverse events occurring within the 12 week post final dose period will be followed to resolution/stabilisation. Pregnancies occurring

within the 12-week post final dose will be followed up until end of subject's participation in the study or until the outcome of pregnancy is known (whichever is later).

6.5.2 Follow-up of unresolved adverse events

Any AEs that are unresolved at the subject's last visit in the study are followed up by the study staff for as long as medically indicated. The Sponsor retains the right to request additional information for any subject with ongoing AE(s)/SAE(s) at the end of the study, if judged necessary.

6.5.3 Variables

The following variables will be collected for each AE:

- AE (verbatim)
- The date when the AE started and stopped. For infusion-related AEs, in addition to date, time when the AE started and stopped must be collected
- Maximum intensity
- Whether the AE is serious or not
- Investigator causality rating against the IP (yes or no)
- Action taken with regard to IP
- Outcome of AE

In addition, the following variables will be collected for SAEs:

- Onset Date (Date AE met criteria for serious AE)
- Detection Date (Date Investigator became aware of serious AE)
- AE is serious due to:
 - (a) Death
 - Date of death
 - Autopsy performed
 - Primary/secondary cause of death

- (b) Life-threatening
- (c) In-patient hospitalisation or prolongation of existing hospitalisation
 - Date of hospitalisation
 - Date of discharge
- (d) Congenital abnormality or birth defect
- (e) Important medical event
 - Description of AE
 - Investigator causality assessment to concomitant medications
 - Investigator causality assessment to study procedures (yes or no)

It is important to distinguish between serious and severe AEs. Severity is a measure of intensity, whereas seriousness is defined by the criteria defined in Section 6.2. An SAE is an AE that fulfils one or more of the following criteria:

- Results in death
- Is immediately life-threatening
- Requires in-patient hospitalisation or prolongation of existing hospitalisation
- Results in persistent or significant disability/incapacity or substantial disruption of the ability to conduct normal life functions
- Is a congenital abnormality or birth defect
- Is an important medical event that may jeopardise the subject or may require medical intervention to prevent one of the outcomes listed above.

For further guidance on the definition of a SAE, see [Appendix A](#).

It is important to distinguish between serious and severe AEs. Severity is a measure of intensity whereas seriousness is defined by the criteria in Section 6.2. An AE of severe intensity need not necessarily be considered serious. For example, nausea that persists for several hours may be considered severe nausea, but not a SAE unless it meets the criteria shown in Section 6.2. On the other hand, a stroke that results in only a limited degree of disability may be considered a mild stroke but would be a SAE when it satisfies the criteria

shown in Section 6.2. The Investigator should provide an assessment of the severity of each AE/SAE.

6.5.4 Causality collection

The Investigator will assess causal relationship between IP and each AE, and answer ‘yes’ or ‘no’ to the question ‘Do you consider that there is a reasonable possibility that the event may have been caused by the IP?’

For SAEs causal relationship will also be assessed for any other medication and study procedures. Note that for SAEs that could be associated with any study procedure the causal relationship is implied as ‘yes’.

A guide to the interpretation of the causality question is found in [Appendix A](#).

6.5.5 Adverse events based on signs and symptoms

All AEs spontaneously reported by the subject or care provider or reported in response to the open question from the study personnel: ‘Have you had any health problems since the previous visit/you were last asked?’, or revealed by observation will be collected and recorded in the CRF. When collecting AEs, the recording of diagnosis is preferred (when possible) to recording of a list of signs and symptoms. However, if a diagnosis is known and there are other signs or symptoms that are not generally part of the diagnosis, the diagnosis and each sign or symptom will be recorded separately.

6.5.6 Adverse events based on examinations and tests

The results from protocol mandated laboratory tests and vital signs will be summarised in the CSR. Deterioration as compared to baseline in protocol mandated laboratory values, vital signs, ECGs, and other safety assessments should therefore only be reported as AEs if they fulfil any of the SAE criteria or are the reason for discontinuation of treatment with the IP.

If deterioration in a laboratory value/vital sign is associated with clinical signs and symptoms, the sign or symptom will be reported as an AE and the associated laboratory result/vital sign will be considered as additional information. Wherever possible the reporting Investigator will use the clinical, rather than the laboratory term (eg, anaemia versus low haemoglobin value). In the absence of clinical signs or symptoms, clinically relevant deteriorations in non-mandated parameters should be reported as AE(s).

Deterioration of a laboratory value, which is unequivocally due to disease progression, should not be reported as an AE/SAE.

Any new or aggravated clinically relevant abnormal medical finding at a physical examination as compared with the baseline assessment will be reported as an AE (or SAE, as appropriate).

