3.9 Discontinuation of investigational product

3.9.1 Criteria for discontinuation of investigational product due to worsening LN or SLE (at any time)

Blinded IP will be discontinued in subjects who meet pre-defined criteria for worsening LN or SLE. Subjects may receive rescue treatment as clinically indicated. Subjects who had their IP discontinued will be followed according to the study schedule. These subjects will be followed until Week 52 (or for a minimum of 12 weeks after last dose of IP for subjects for whom IP was discontinued within 12 weeks prior to Week 52). If discontinuation occurs during the second year extension period, subjects will be followed until Week 104 (or for a minimum of 12 weeks after last dose of IP for subjects for whom IP was discontinued within 12 weeks prior to Week 104).

- >30% decrease in eGFR compared to baseline due to LN and eGFR <60 mL/min/1.73 m² (on two independent samples) or
- Increase in renal or extra-renal lupus activity requiring prohibited systemic immunosuppressive treatment (eg, cyclophosphamide, rituximab, belimumab)
- Receipt of >1 methylprednisolone pulse after the day of randomisation
- Receipt of any methylprednisolone pulse after Week 8
- The IP will be discontinued if MMF is discontinued and another immunosuppressant is initiated

3.9.2 Criteria for discontinuation of investigational product for worsening of LN or SLE at Week 12 and Week 24

- eGFR <75% of baseline and <60 mL/min/1.73 m² (on two independent samples) or
- Nephrotic range UPCR (confirmed by a second measurement at least two weeks after the first measurement):
 - Subjects with 24-hour UPCR ≤3 mg/mg at baseline will be withdrawn if 24-hour UPCR increases by >50% from baseline to >3.5 mg/mg

- Subjects with 24-hour UPCR >3 mg/mg at baseline will be withdrawn if 24-hour UPCR at Week 24 >3.5 mg/mg and there is $<60\%$ improvement from baseline or
- Inability to adhere to corticosteroids requirements:
 - Inability to reduce OCS to ≤ 15 mg/day prednisone-equivalent at Week 12
 - Inability to reduce OCS to <15 mg/day by Week 24

Subjects who exceed the maximum daily OCS dose at the Week 12 or Week 24 visits may continue to receive IP if the current dose is part of a temporary increase in OCS dose (eg, protocol-allowed burst and taper). Subjects who cannot be returned to their pre-increase dose within 14 days from the start of the increase will have their IP discontinued at the next visit.

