6.5.7 Disease progression/worsening of systemic lupus erythematosus and lupus nephritis

Disease progression can be considered as a worsening of a subject's condition attributable to SLE or LN. It may be an increase in the activity or severity of the existing manifestations of LN or SLE or the appearance of new manifestations. Disease progression should not be reported as an AE unless it fulfils criteria for SAE (please see Section 6.2 for definition of SAE). However, worsening of SLE or LN will be recorded in the disease assessment tools (SLEDAI-2K, PGA and PtGA).

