6.6 Reporting of serious adverse events

All SAEs have to be reported, whether or not considered causally related to the IP, or to the study procedure(s). All SAEs will be recorded in the CRF. All safety forms and supportive documentation include laboratory tests, imaging reports, diagnostic test results, biopsy reports, and discharge summaries is to be sent to the Sponsor's delegate Medical Services.

If any SAE occurs in the course of the study, then the Investigator or other site personnel inform the appropriate AstraZeneca representatives within one day, ie, immediately but **no later than 24 hours** of when he or she becomes aware of it.

The designated AstraZeneca representative works with the Investigator to ensure that all the necessary information is provided to the AstraZeneca Patient Safety data entry site or designee **within 1 business day** of initial receipt for all SAEs.

For fatal or life-threatening AEs where important or relevant information is missing, active follow-up is undertaken immediately. Investigators or other site personnel should inform AstraZeneca representatives of any follow-up information on a previously reported SAE immediately but **no later than 24 hours** of when he or she becomes aware of it.

Once the Investigators or other site personnel indicate an AE is serious in the DataLabs system, an automated e-mail alert is sent to the designated AstraZeneca representative.

If the DataLabs system is not available, then the Investigator or other study site personnel reports the SAE to the Sponsor's delegate Medical Services on the study specific paper SAE form by telephone, FAX, or e-mail. The SAE report form must be completed in the electronic system as soon as the system is available again.

SAE information should be sent to the Sponsor's delegate Medical Services.

The Sponsor's delegate Medical Services, on behalf of AstraZeneca, is responsible for reporting certain SAEs as expedited safety reports to applicable regulatory authorities, Ethics Committees (ECs), and participating Investigators, in accordance with International Conference on Harmonisation (ICH) Guidelines and/or local regulatory requirements. Sponsor/Designee may be required to report certain SAEs to regulatory authorities within 7

calendar days of being notified about the event; therefore, it is important that Investigators submit additional information requested by Sponsor/Sponsor's delegate as soon as it becomes available.

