4.2.6.1 Adverse Events

If not stated otherwise, all summaries described below will be presented separately for

- AEs during treatment
- AEs during follow-up

For summaries during follow-up, only subjects with any study documentation after the date of last dose of IP + 28 days will be considered.

An overall summary of subjects with at least one AE in the following categories will be presented, and will include the event rate per 100 subject years, and total exposure in years for each treatment group:

- Any AE
- Any acute AEs
This category will not be included in the summary during follow-up.
- Any AE with outcome = death
- Any SAE (including events with outcome = death)
- Any AE leading to discontinuation of IP
 - This category will not be included in the summary during follow-up.
- Any AE related to IP by investigator's judgement
- Any AE of severe intensity
- Any AESI
 - Any AESI of non-opportunistic serious infections
 - Any AESI of opportunistic infections
 - Any AESI of anaphylaxis
 - Any AESI of malignancy
 - Any AESI of herpes zoster
 - Any AESI of tuberculosis
 - Any AESI of influenza
 - Any AESI of vasculitis (non-SLE)
 - Any AESI of major acute cardiovascular events (MACE as adjudicated)
- Any other significant AE

The number and percentage of subjects with at least one AE (i.e. multiple occurrences of an AE in 1 subject will only be counted once) will be summarised by MedDRA system organ class and preferred term (unless specified otherwise) for the following AE categories. These summaries will also include the event rate per 100 subject years and total exposure in years for each treatment group (unless specified otherwise).

- Any AE
- Any AE above reporting threshold of 2% of subjects in any treatment group in the full analysis set.
This summary will be presented by preferred term for AEs during treatment only.
- Any non-serious AE above reporting threshold of 5% of subjects in any treatment group in the full analysis set
This summary will not include the event rate per 100 subject years and total exposure in years.
- Any SAE with outcome = death
This summary will be presented for SAEs with an outcome of death during the treatment and follow-up periods combined.
- Any SAE (including events with outcome = death)
- Any AE leading to discontinuation of IP
This summary will be presented for AEs during treatment only.
- Any AE by relationship to IP (yes, no)

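### Protocol 6.5.6 bars reporting of laboratory worsening due to lupus nephritis even when it is serious, which contradicts 6.5.7 and 6.6

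*Protocol*

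**What the plan says.** Four places in the Protocol bear on the same event.

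- Section 6.5.6, first paragraph: deterioration in protocol-mandated laboratory values, vital signs and similar assessments should "only be reported as AEs if they fulfil any of the SAE criteria or are the reason for discontinuation of treatment with the IP".
- Section 6.5.6, third paragraph: "Deterioration of a laboratory value, which is unequivocally due to disease progression, should not be reported as an AE/SAE".
- Section 6.5.7: "Disease progression can be considered as a worsening of a subject's condition attributable to SLE or LN", and "Disease progression should not be reported as an AE unless it fulfils criteria for SAE". Laboratory-defined LN worsening is not carved out.
- Section 6.6: every SAE is to be reported, whatever its cause, and within 24 hours of the site becoming aware of it.

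The SAE criteria in 6.2 include "Requires in-subject hospitalisation or prolongation of existing hospitalisation". Section 3.9.1 lists an LN-attributed laboratory change among the reasons for stopping IP: a confirmed "decrease in eGFR compared to baseline due to LN and eGFR" below a stated level. Section 3.9.2 adds eGFR and 24-hour UPCR criteria at Weeks 12 and 24. SAP 4.2.6.1 tabulates SAEs by treatment group, and also "Any AE leading to discontinuation of IP".

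**The concern.** The trial treats LN, so laboratory evidence of LN worsening is an expected event, and attribution of that worsening to LN is written into one of the stopping criteria. The same attribution brings the third paragraph of 6.5.6 into play. If that paragraph is applied as written, a serious renal deterioration seen mainly in creatinine, eGFR or proteinuria need not reach the sponsor as an SAE.

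Two things are at stake. The first is the 24-hour SAE report and any expedited report that follows from it. The second is the comparability of the SAE table: about 95 sites are planned, and the count in each arm can depend on which sentence a site follows. Because the events are failures of control of the treated disease, their frequency may differ between arms.

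**Working it through.** No formula applies to the contradiction itself. The check sets the rules side by side for two cases of laboratory worsening that is unequivocally due to LN.

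| Protocol text | Case 1: meets an SAE criterion | Case 2: non-serious, but the reason IP is stopped |
|---|---|---|
| 6.5.6, first paragraph | condition for reporting met | condition for reporting met |
| 6.5.6, third paragraph | do not report as AE or SAE | do not report as AE or SAE |
| 6.5.7 | report | do not report |
| 6.6 | report | silent |

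**Case 1.** The third paragraph of 6.5.6 and section 6.6 cannot both be followed. It does not help to say that the third paragraph takes the event out of the SAE definition. Section 6.1 counts an abnormal laboratory finding and the deterioration of an existing condition as possible AEs, and 6.2 makes an AE serious once a criterion is met, so the event is still an SAE by definition. The third paragraph only says not to report it. Section 6.5.7, on its ordinary reading, calls for reporting once the criteria are met. Even if it is read strictly as a permission, 6.6 supplies the duty.

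**Case 2.** The first paragraph is worded as a restriction (report only if). Meeting its condition permits a report but does not require one. The third paragraph and 6.5.7 agree on not reporting. A site that does not report follows all three texts, so there is no contradiction here.

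**Scale of one event.** The planned size is 50 per arm (Protocol 8.2), so 100 in the pooled anifrolumab group. One subject reclassified changes an arm's SAE percentage by 1/50 = 2 points, or the pooled percentage by 1/100 = 1 point. The number of such subjects is not given and cannot be derived.

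**The case against.** The best defence is that the two sections address different things. The third paragraph of 6.5.6 concerns a laboratory value, and 6.5.7 concerns the subject's condition. Section 6.5.5 prefers a diagnosis to a list of signs, and the second paragraph of 6.5.6 prefers the clinical term to the laboratory one. On that reading a hospitalised LN worsening is reported as the LN event, and the creatinine is simply not a second SAE. This is workable, and many sites may do it. But the text does not say so, the third paragraph names SAEs explicitly, and the first paragraph of the same section treats laboratory deterioration as able to meet SAE criteria. The defence narrows the problem without removing it.

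A second defence is that renal worsening would still be visible elsewhere. The flare instrument records hospitalisations due to LN (5.2.8), a medical review team looks at LN, AE and laboratory data together (9.2.4), SAEs are reconciled between databases (9.4), and chemistry is summarised by visit (SAP 4.2.6.2). That stands against any inference that serious renal events would vanish from the data. None of these places the event in the SAE table or guarantees a 24-hour report.

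A reader might also infer that the AE-leading-to-discontinuation table is contradictory in the same way. The documents do not support that. Besides the agreement in Case 2, stops for LN worsening (3.9.1 and 3.9.2) are kept apart from stops for other reasons, among which an adverse event is listed (3.9.4). SAP 4.2.5.1 already tabulates IP discontinuations by reason. An extra row in SAP 4.2.6.1 is not needed.

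Appendix A, cited for SAE guidance, is not in the supplied text and might help. The conflict in the body of the Protocol would remain.

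**Conclusion.** The contradiction holds for serious events: the third paragraph of 6.5.6 conflicts with 6.5.7 and 6.6, and sits uneasily with the first paragraph of its own section. It applies to LN worsening defined by laboratory values that meets an SAE criterion, and is sharpest where no separate clinical diagnosis is reported.

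The documents support saying that such events can be handled differently between sites. They do not show that they will be, and they give no frequency, so no by-arm effect can be estimated. For non-serious IP stops the text can be read consistently as recording the stop under its discontinuation reason, and what remains is an ambiguity. The conclusion assumes that no appendix or site guidance outside the supplied text already sets the order of precedence.

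**What to change.** Reconcile the passages by adding a clause to the third paragraph of 6.5.6 that makes its exemption subject to 6.5.7 and 6.6, so that it covers only laboratory deterioration that meets no SAE criterion. Repeat the rule in the eCRF completion guideline.

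As a secondary clarification, state once how a non-serious IP stop under 3.9.1 or 3.9.2 is recorded: either under the discontinuation reason already tabulated in SAP 4.2.5.1, or as an AE.

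The cost is a sentence or two in the Protocol and a line in the eCRF guideline. No new data, assessment or SAP table is needed, and no stopping criterion changes.
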